8.2.1.4.1 Reporting of SAEs to the IRB

The investigator will receive prompt notification of SAEs, with the use of the study product, that are both unexpected and related, or any finding that suggests a significant risk for patients. The investigator will promptly inform the IRB of the notification and insert the notification in the Investigator's Regulatory Binder in accordance with local regulations.

All applicable expedited safety reports will be forwarded, by Ironwood, to the investigator.

The investigator will inform Ironwood of any local regulatory or IRB requirements not covered by the procedures in this or the prior section.

8.2.1.4.2 Reporting of Pregnancy

Any female patient who becomes pregnant while participating in the study will be withdrawn from the study.

Information on any pregnancies in female patients, or the female partner of a male patient, will be collected from the Screening Visit until the completion of the EOS Follow-up Phone Call.

If the patient or the female partner of a male patient becomes pregnant after receiving study drug during the course of study, the investigator will collect and record the pregnancy information on the Pregnancy Reporting Form and submit it to PPD within 24 hours of learning of the pregnancy. (Note: If the female partner of a male patient becomes pregnant, the investigator must attempt to obtain consent to collect pregnancy information [including status of the newborn, if applicable] before reporting information to Ironwood). If not all information on the Pregnancy Reporting Form is available at the time of the initial report, follow-up Pregnancy Reporting Forms will be completed and submitted within 24 hours of becoming aware of new information.

The investigator is required to attempt follow-up on the pregnancy until the completion of the pregnancy. Information on the status of the mother and newborn will be forwarded to PPD within 24 hours of the investigator becoming aware. Generally, follow-up will be no longer than 6 to 8 weeks following the estimated delivery date.

While pregnancy itself is not considered to be an AE, any pregnancy complication or elective termination of a pregnancy for medical reasons will be an SAE and reported as such. A spontaneous abortion is always considered to be an SAE and will be reported as such. Furthermore, any SAE occurring as a result of a post-study pregnancy and considered reasonably related to the investigational product by the investigator, will be reported to PPD using the hard-copy SAE form as described in Section 8.2.1.4. While the investigator is not obligated to actively seek this information in former study participants, he or she may learn of an SAE through spontaneous reporting.

8.2.2 Clinical Laboratory Determinations

See below for the list of clinical laboratory tests to be performed and refer to the [Schedule of Evaluations](#) for the timing and frequency. All protocol-required laboratory assessments, as defined below, must be conducted in accordance with the laboratory manual and the [Schedule of Evaluations](#).

The tests detailed below will be performed (additional tests may be performed at any time during the study as determined necessary by the investigator or as required by local regulations):

- **Hematology:** Absolute and differential white blood cell count, erythrocyte count, hemoglobin, hematocrit, platelet count, and red blood cell indices (mean corpuscular volume, mean corpuscular hemoglobin, and mean corpuscular hemoglobin concentration)
- **Chemistry:** Sodium, magnesium, potassium, calcium, chloride, glucose, blood urea nitrogen, creatinine, total protein, alkaline phosphatase, albumin, total bilirubin, aspartate aminotransferase, alanine aminotransferase, bicarbonate, phosphate, cholesterol, and uric acid

- **Other:** Urine drug screening (cocaine, barbiturates, amphetamines, opiates, benzodiazepine, alcohol, and cannabinoids) (Screening Visit only). By definition, a positive drug screen (including testing positive for marijuana in states where marijuana is legalized) is clinically significant and, therefore, exclusionary.
- **Pregnancy test:** Serum human chorionic gonadotropin pregnancy test (for women of childbearing potential only) should be conducted at the Screening Visit and Week 12/EOT Visit. A negative urine pregnancy test must be documented at the Randomization Visit for women of childbearing potential to be eligible for randomization and dosing with study drug. Positive results on the pregnancy test will exclude a patient from participating or continuing in the study.

The investigator must review each laboratory report, document this review, and record any clinically relevant changes occurring during the study in the AE section of the eCRF. The laboratory reports must be filed with the source documents. All laboratory tests with abnormal values considered clinically significant during participation in the study should be repeated until the values return to normal or baseline or are no longer considered clinically significant by the investigator or Medical Monitor. If such values do not return to normal/baseline within a period of time judged reasonable by the investigator, the etiology should be identified and the Sponsor notified. If laboratory values from non-protocol specified laboratory assessments performed at the institution's local laboratory require a change in patient management or are considered clinically significant by the investigator (eg, SAE or AE or study drug discontinuation), the results must be recorded in the eCRF.

8.2.3 Vital Signs

Vital sign measurements will be performed as outlined in the [Schedule of Evaluations](#). Oral temperature, pulse rate, respiratory rate, and systolic and diastolic blood pressure (BP) will be assessed with the patient in a seated position. BP and pulse measurements will be assessed with a completely automated device; manual techniques will be used only if an automated device is not available.

BP and pulse measurements should be preceded by at least 5 minutes of rest for the patient in a quiet setting without distractions (eg, television, cell phones).

8.2.4 Physical Examination

A complete physical examination will be performed as outlined in the [Schedule of Evaluations](#), by the investigator or a licensed health professional listed on Form FDA 1572. Any physical examination abnormality that the investigator considers to be potentially clinically significant and changed from the baseline will be reported as an AE. A complete physical examination will include, at a minimum, assessment of the general appearance of the patient and the HEENT (head, eyes, ears, nose, and throat), cardiac, respiratory, gastrointestinal, musculoskeletal, neurological, and dermatological systems. Height (only at screening) and weight will also be measured and recorded.

Rectal examinations should be performed at the discretion of the investigator; the purpose of the rectal examination is to rule out pathologies that might be caused by obstruction. For all physical examinations, the breast and genitourinary examinations are not required.

8.2.5 Medical History

A complete medical history, including disease-specific history, will be provided by the patient at the Screening Visit.

As part of their disease-specific history, patients will be asked about any prior IBS diagnosis.

Patients will be enrolled based on the Rome IV criteria for IBS-D, as detailed in Section [6.1](#) and described below.

Patient reports recurrent abdominal pain, on average at least 1 day/week during the 3 months before the diagnosis, with the onset at least 6 months before the diagnosis, associated with 2 or more of the following features:

- a. Related to defecation
- b. Associated with a change in frequency of stool
- c. Associated with a change in form (appearance) of stool

According to the Rome IV criteria, patients are subtyped as IBS-D if they have >25% of BMs with BSFS score of 6 or 7 and <25% of BMs with BSFS score of 1 or 2, based on stool form on days with at least 1 abnormal BM.

8.2.6 Required Investigator Consultation with the Patient

Patients will be allowed use of loperamide on an as-needed basis to control their diarrhea. Throughout the Pretreatment and Treatment Periods, the eDiary will send automated alerts to the investigator if patients experience constipation with excessive use of loperamide or diarrhea that is not well managed with the use of loperamide, as described below.

If a patient reports no BMs for ≥ 3 consecutive days with daily use of loperamide, the investigator must review the use of loperamide and pattern of constipation with the patient. An unscheduled visit to further evaluate the patient should be arranged if deemed necessary by the investigator. The decision to continue, interrupt, or permanently discontinue study drug will be left to the discretion of the investigator on a patient-by-patient basis.

If the eDiary alert indicates that a patient took ≥ 8 unit doses (≥ 16 mg) of loperamide in a 24-hour period for ≥ 5 consecutive days, the investigator must review the use of loperamide and pattern of diarrhea with the patient. An unscheduled visit to further evaluate the patient should be arranged if deemed necessary by the investigator. The decision to continue, interrupt, or permanently discontinue study drug due to excessive use of loperamide will be left to the discretion of the investigator on a patient-by-patient basis.

9. DATA QUALITY ASSURANCE

9.1 DATA MONITORING

Before any patient enters the study, a representative of Ironwood or its authorized designee will meet with the investigator and his/her staff to review the procedures to be followed while conducting the study and to train them on recording the data on the eCRFs using the electronic data capture (EDC) system.

After the first patient signs the ICF, the Ironwood representative, a site monitor, will periodically monitor the progress of the study by conducting monitoring visits. This site monitor will also be able to review the status of data queries remotely, possibly warranting more frequent communication with the investigator and his/her staff. The investigator and his/her staff will be responsible for reviewing eCRFs, resolving data queries generated by the site monitor via the system, providing missing or corrected data, approving all changes performed on his/her data, and endorsing the patient data within the EDC system. This approval method will include applying an electronic signature, which is a uniquely assigned username and password that together will represent a traditional handwritten signature.

9.2 DATA RECORDING AND DOCUMENTATION

All data collected in the context of this study will be stored and evaluated in such a way as to guarantee patient confidentiality in accordance with the legal stipulations applying to confidentiality of data. Study records (eg, essential documents [commonly called regulatory documents], correspondence) will be retained at the study center, along with adequate source documentation, according to FDA and ICH requirements. All study records must be available for inspection by Ironwood, its authorized designee, and the FDA.

Data collection will involve the use of the [REDACTED], to which only authorized personnel will have access. In addition to periodic monitoring occurring within the system by Sponsor site monitors, programmatic edit checks and manual review procedures will be used to review the data for completeness, logic, and adherence to the study protocol. As a result of this monitoring and these checks, data queries may be electronically issued to the clinical study centers and electronically closed by those centers. The identifying information (assigned username, date, and time) for both the originator of the query (if created during the monitoring process) and the originator of the data change (if applicable), as well as the investigator's approval of all changes performed on his/her patients' data, will be collected.

10. STATISTICAL METHODS AND DETERMINATION OF SAMPLE SIZE

10.1 ANALYSIS POPULATIONS

10.1.1 Screened Population

The Screened Population consists of all patients who had a Screening Visit (Visit 1) and were assigned a PID number.

10.1.2 Intent-to-Treat Population

The Intent-to-Treat (ITT) Population consists of all randomized patients.

10.1.3 Safety Population

The Safety Population consists of all patients who received at least one dose of study drug.

10.2 GENERAL METHODS

Efficacy analyses will be performed on the ITT Population for all outcomes reported during the Treatment Period using treatment group assigned at the Randomization Visit. Unless otherwise specified, all confidence intervals (CIs) will be 2-sided and with a confidence level of 95%. No adjustments will be made for multiplicity in the conduct of comparisons among the MD-7246 doses relative to placebo for the key efficacy endpoints, or in the analysis of the additional efficacy endpoints or exploratory endpoints. Safety analyses will be performed using descriptive summaries based on the Safety Population and on actual treatment received.

For analysis of continuous parameters (eg, change from baseline), descriptive statistics (n, mean, standard deviation [SD], median, and range) will be calculated and presented for each treatment group. For categorical parameters (eg, responder vs. non-responder), the number and percentage of each category will be calculated and presented for each treatment group. Percentages will be based on the total number of non-missing values; the number missing will be presented, but without a percentage.

10.2.1 Patient Disposition

Screen failures (ie, patients who entered the Screening Period but not the Pretreatment Period) and pretreatment failures (ie, patients who entered the Pretreatment Period but were not randomized) and reason for failure will be tabulated.

Patient counts for the ITT Population will be provided by study center and geographic region.

Descriptive summaries will be presented for the ITT Population, the Safety Population, for those who completed the Treatment Period and for those who prematurely discontinued during the Treatment Period, along with the reason for premature discontinuation as recorded on the study completion form. Additionally, similar summaries will be provided for those who completed the study (ie, completed the Treatment Period and 2-week Posttreatment Period) and for those who discontinued prior to completing the study.

10.2.2 Demographics and Baseline Characteristics

Demographic parameters (age, age group, race, ethnicity, sex), and baseline characteristics (weight; height; and body mass index, calculated as $\text{weight in kg}/[\text{height in m}]^2$) will be summarized descriptively for the Safety and ITT Populations. Baseline efficacy and bowel parameters (including abdominal pain, abdominal bloating, abdominal discomfort, abdominal cramping, BM frequency, urgent BM frequency, BSFS score, stool consistency) will be summarized descriptively for the ITT Population.

10.2.3 Protocol Deviations

Protocol deviations and Important Protocol Deviations (IPD) will be identified and documented for all ITT patients prior to unblinding. IPDs will be determined based on blinded review of all protocol deviations and protocol deviation categories. IPD categories include, but are not limited to:

- Those who entered the study even though they did not satisfy the entry criteria
- Those who developed withdrawal criteria during the study but were not withdrawn
- Those who received the wrong treatment or incorrect dose
- Those who received an excluded concomitant treatment

10.2.4 Prior and Concomitant Medicines

Prior and concomitant medicines will be classified using the most current version of the WHO Drug Dictionary available at the start of the study (or newer).

Prior medicines are defined as any medicines taken prior to the date of first dose of study drug. Concomitant medicines are defined as any medicines taken on or after the date of first dose of study drug during the Treatment Period. Posttreatment medicines are defined as any medicines started after the date of last dose of study drug for the Treatment Period.

Both prior and concomitant medicine use, classified by therapeutic class, will be summarized by treatment group for the ITT Population. Multiple medicines used by a patient in the same category (based on Anatomical-Therapeutic-Chemical classification) will be counted only once.

Posttreatment medicines will be presented in data listings.

10.3 EXTENT OF EXPOSURE AND TREATMENT COMPLIANCE

10.3.1 Exposure to Study Drug

Exposure to study drug, calculated as the number of days from the date of first dose taken to the date of last dose taken, will be summarized by treatment group for the Safety Population.

10.3.2 Measurement of Treatment Compliance

Dosing compliance for a specified period is defined as the total number of tablets actually taken by a patient during that period divided by the number of tablets that were expected to be taken during the same period, multiplied by 100. The total number of tablets actually taken will be calculated based on the following equation: total number of tablets dispensed – (number of tablets returned + number of tablets lost). The total number of tablets expected to be taken during a specified period equals the number of days in the period, multiplied by 4.

Descriptive statistics for study drug compliance for the Treatment Period overall, and for each of the 3 consecutive 4-week periods in the Treatment Period (consistent with study drug dispensing) will be presented for the Safety Population.

10.3.3 eDiary Compliance

eDiary compliance will be based on the percentage of complete eDiary entries made by a patient. A complete eDiary entry is defined as one in which the patient responds to every eDiary question asked in the evening report on that day. The questions that are asked weekly will not be included in the determination of a complete entry. The percentage of complete eDiary entries will be calculated as 100 times the number of completed evening reports divided by the total number of days in the study period (Pretreatment and Treatment).

Descriptive statistics for eDiary compliance (%) and the patients with $\geq 80\%$ / $< 80\%$ complete eDiary entries during the Pretreatment and Treatment Periods will be presented.

10.4 EFFICACY ANALYSES

All efficacy analyses to address the objectives of the study will be based on the ITT Population. Exploratory analyses to address the exploratory objective of the study also will be based on the ITT Population.

Baseline values for efficacy and exploratory parameters are derived from the eDiary and eCRF data collected in the Pretreatment Period, specifically, the period of time from 14 days prior to randomization up to the time of randomization. Baseline values for patient symptom severity parameters (eg, abdominal symptoms [pain, bloating, discomfort, cramping]) will be the average of the non-missing severity scores reported during this period. The baseline BM and urgent BM weekly rates will be derived based on the number of BMs and urgent BMs a patient had during this period. Baseline BSFS score and stool consistency will be calculated as the average of the non-missing values reported by the patient during this period.

Study centers will be pooled together by geographic region (details to be provided in the Statistical Analysis Plan [SAP]). In lieu of study center, geographic region will be used in analyses adjusting for center-to-center variability.

Sensitivity analyses of the key endpoints will include, but are not limited to, a multiple imputation approach. If the normality assumption of the errors is violated for the key mixed model with repeated measures (MMRM) or analysis of covariance (ANCOVA) analyses, ranked or other appropriate analyses will be applied.

All hypothesis testing will be performed at a 2-sided 0.05 significance level. No adjustment for multiplicity will be applied.

10.4.1 Key Efficacy Endpoints

The 2 key efficacy endpoints are:

- **Change from Baseline in Abdominal Pain at its Worst at Each Week**

The weekly abdominal pain at its worst score is the average of the non-missing abdominal pain scores during each week (Weeks 1-12) in the study. The baseline abdominal pain score is the average of the non-missing abdominal pain scores during the last 14 days of the Pretreatment Period and the day of the Randomization Visit reported prior to randomization. Change from baseline will be calculated for each week as the weekly score minus the baseline score.

- **6/12 Week Abdominal Pain 30% Responder**

A 6/12 Week Abdominal Pain 30% Responder is a patient who meets the Weekly Abdominal Pain 30% Responder criteria for at least 6 out of the 12 weeks of the Treatment Period. A Weekly Abdominal Pain 30% Responder is a patient who has a decrease from baseline of at least 30% in the mean abdominal pain at its worst score for that week. If a patient did not enter information into the eDiary on at least 4 days for a particular Treatment Period week, the patient will not be considered a Weekly Abdominal Pain 30% Responder for that week.

10.4.2 Key Efficacy Analysis

Comparisons between the MD-7246 dose groups and placebo with regard to the change from baseline in abdominal pain over the Treatment Period will be evaluated employing a MMRM framework with week (categorical), treatment, geographic region, and week-by-treatment fixed effects, patient as the random effect, and baseline value as a covariate. An unstructured covariance structure will be utilized. Descriptive statistics, for the overall Treatment Period effect, based on the MMRM model will include least-squares (LS) mean change from baseline for each treatment, the LS mean difference between each MD-7246 dose and placebo, corresponding 95% CIs, and the p-value associated with the comparison. In addition, weekly treatment differences between each MD-7246 group and placebo will be provided using the same MMRM model defined above.

For the 6/12 Week Abdominal Pain 30% Responder endpoint, the proportion of responders in each MD-7246 group will be compared to the proportion of responders in the placebo group using a Cochran-Mantel-Haenszel (CMH) test controlling for geographic region. The number and percent of responders, the difference in responder rates between each MD-7246 group and the placebo group, the odds ratio relative to placebo, all corresponding 95% CIs, and the p-value associated with the CMH test will be presented.

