10.4.6 Exploratory Analysis

Exploratory change-from-baseline endpoints will be analyzed utilizing the same methods as described in Section 10.4.2 for the key efficacy analysis. BM-related Symptom Change will be analyzed utilizing an MMRM framework with week (categorical), treatment, geographic region, and week-by-treatment fixed effects, and patient as the random effect. An unstructured covariance structure will be utilized. Pairwise comparisons between each treatment group and placebo will be performed for the overall Treatment Period effect. MMRM-associated statistics, as defined in Section 10.4.2 for the key efficacy change-from-baseline endpoint, will be presented.

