10.8 DETERMINATION OF SAMPLE SIZE

In a previously conducted Phase 2b trial utilizing MD-7246 (MCP-103-204), the SD for the change from baseline to Week 12 in abdominal pain at its worst ranged from 2.32 to 2.88. Assuming a clinically meaningful treatment difference between MD-7246 and placebo of 1.0 for the mean change from baseline to Week 12 in abdominal pain, an SD of 2.4, and 92 patients per treatment group (368 patients total), the estimated power is approximately 80% to detect a difference between each MD-7246 dose and placebo at a 2-sided significance level of 0.05 using a 2-sample t-test.

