7.8.9.2. Analyses of the Key Efficacy Endpoints

Change from Baseline in Abdominal Pain Through the Treatment Period

The overall treatment effect will be evaluated via the comparison between the MD-7246 dose groups and placebo with regard to the weekly change from baseline (CFB) in abdominal pain using a MMRM model, including the weekly CFB score in abdominal pain as dependent variable and treatment, visit week (categorical), and treatment-by-week as fixed effects, patient as a random effect, and the baseline value as a continuous covariate. An unstructured covariance matrix will be used for the MMRM analysis, unless the model does not converge, in which case the compound symmetry will be used.

In this MMRM, a patient in mITT population without any postbaseline abdominal pain score at its worse will be considered missing. For patients with postbaseline abdominal pain scores, at any particular week, if there are fewer than 4 daily scores available, the weekly change from baseline will be considered as missing. Weeks after the treatment discontinuation will be considered as missing.

Descriptive statistics for the overall treatment effect based on the MMRM model will include the least-squares (LS) mean difference between each MD-7246 dose and placebo, LS mean change from baseline for each treatment, their corresponding 95% CIs, and the p-values associated with the comparisons to placebo. In addition, LS Means for the weekly treatment differences between each MD-7246 group and placebo will also be provided with the same set of statistics derived from the same MMRM model defined above and will be plotted based on the MMRM estimates.

Additionally, the non-model based descriptive statistics for the corresponding change from baseline (overall or weekly) will be provided by treatment group in the same tables for the MMRM estimates. Among them, the overall change from baseline is defined as the average of all non-missing post baseline daily scores during the Treatment Period minus the baseline abdominal pain score. The cumulative distribution for the overall change from baseline during the entire treatment period will be summarized and plotted by treatment group.

6/12 Week Abdominal Pain 30% Responder

For the 6/12 Week Abdominal Pain 30% Responder endpoint, the proportion of responders in each MD-7246 treatment group will be summarized and compared to the proportion of responders in the placebo group using a CMH test. The number and percentage of responders,

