7.8.9.4. Additional Efficacy Endpoints and Analyses

The following endpoints are defined similarly to the Change from Baseline in Abdominal pain, for its overall and weekly. They will be analyzed using similar MMRM model and the non-model based summary statistics for the Change from Baseline in Abdominal Pain (through the Treatment Period and at each week):

- Change from Baseline in Abdominal Discomfort through the Treatment Period and at each week
- Change from Baseline in Abdominal Bloating through the Treatment Period and at each week
- Change from Baseline in Abdominal Cramping through the Treatment Period and at each week
- Treatment Satisfaction through Treatment period and at each week will be summarized and analyzed using MMRM model (without baseline in the model). Treatment Satisfaction is scored weekly on a 5-point scale during the Treatment Period only and no change from baseline is defined for this assessment.

The following 6/12 week responder endpoints are defined in the same manner as the 6/12 Week Abdominal Pain 30% Responder based on their relevant weekly responders. For each week in the Treatment Period, a weekly responder is a patient who satisfies the responder criteria in the change from baseline for that week. If a patient did not enter information into the eDiary on at least 4 days for a particular week during the Treatment Period, the patient will not be considered a weekly responder for that week. A patient who did not have any relevant post baseline assessment will be considered a weekly non-responder for all post baseline weeks, subsequently, will not be a 6/12 week responder. For all weeks after the treatment discontinuation, the patient will be considered as non-responder.

These responder endpoints will be summarized by treatment and the comparison between the active treatment group and placebo will be analyzed using a CMH test. The relevant number and percentage of weekly responders will be summarized by treatment at each week.

- 6/12 Week Abdominal Pain 40% Responder
A 6/12 Week Abdominal Pain 40% Responder is a patient who meets the Weekly Abdominal Pain 40% Responder criteria for at least 6 out of the 12 weeks of the Treatment Period.
- 6/12 Week Abdominal Pain 50% Responder
A 6/12 Week Abdominal Pain 50% Responder is a patient who meets the Weekly Abdominal Pain 50% Responder criteria for at least 6 out of the 12 weeks of the Treatment Period.
- 9/12 Week Abdominal Pain 30% Sustained Responder

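### The key MMRM holds the baseline slope constant over Weeks 1-12; adding a baseline-by-week term is a cheap way to protect a few percent of precision

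*Protocol*

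**What the plan says.** Protocol 10.4.2 models weekly change in worst abdominal pain with week, treatment, region, "week-by-treatment fixed effects, patient as the random effect, and baseline value as a covariate". SAP 7.8.9.2 drops region but treats baseline the same way: "patient as a random effect, and the baseline value as a continuous covariate". SAP 7.2 says in general terms that baseline is a covariate and adds no interaction. Treatment-by-week is therefore the only interaction in the model.

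On covariance, the protocol states: "An unstructured covariance structure will be utilized". The SAP keeps this "unless the model does not converge, in which case the compound symmetry will be used".

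One fit supplies the overall Treatment Period effect and also the by-week results: "weekly treatment differences between each MD-7246 group and placebo will be provided using the same MMRM model defined above". The form is then reused. For discomfort, bloating and cramping, SAP 7.8.9.4 says "They will be analyzed using similar MMRM model"; for the bowel endpoints, protocol 10.4.6 says "Exploratory change-from-baseline endpoints will be analyzed utilizing the same methods as described in Section 10.4.2", and SAP 7.8.10 calls for a similar MMRM for most of them. SAP 7.8.12 uses a similar model for IBS-SSS.

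**The concern.** A single slope is harmless if change relates to baseline in the same way every week. That may not be so here. If improvement builds up over the weeks and is roughly proportional to starting pain, which is the scale the 30% responder endpoint uses, the slope of absolute change on baseline steepens from Week 1 to Week 12.

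The common slope need not settle near the average of the weekly slopes. Generalised least squares gives more weight to weeks with small residual variance. The Week 1 change is measured soon after baseline, so its variance may well be the smallest. The later weeks and the overall contrast would then be adjusted with a slope close to that of Week 1, or even outside the range of the weekly slopes.

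What is at stake is precision, and how well the model corrects for the chance baseline imbalance in this one trial. Once region is removed, baseline is the only prognostic covariate in the model. SAP 7.8.9.3 plans no sensitivity analysis that would show the misfit.

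**Working it through.** **1. The plan's own figure.** Protocol 10.8 and SAP 4 use a difference of 1.0 at Week 12, SD 2.4, 92 per arm and a two-sided 0.05 two-sample t-test. Exact noncentral t gives 80.3%, so the stated figure of about 80% is reproduced. It is an unadjusted figure that takes no credit for baseline.

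**2. Formulas.** Let S be the residual covariance over the 12 weeks, b_t the true baseline slope at week t, and V the baseline variance. For complete data:
- weights w = S⁻¹1 / (1'S⁻¹1), which sum to 1
- common slope β = Σ w_t b_t
- relative extra variance at week t = V (b_t − β)² / S_tt
- relative extra variance, overall effect = V (mean b − β)² / (1'S1/144)

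**3. Inputs.** From the documents: Week 12 change SD 2.4 (range 2.32 to 2.88 in the earlier trial), 92 per arm, and a pain entry range of 4.0 to 9.0. Assumed, because the documents do not give them: baseline SD 1.3 (varied 1.2-1.4); Week 1 change SD 1.3 (varied 1.2-2.4); residual correlation; and slopes from −0.15 at Week 1 to −0.40 at Week 12. Slopes and SDs move from the Week 1 to the Week 12 value in proportion to 1 − exp(−(t−1)/3), so the mean slope is −0.33.

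**4. Results for baseline SD 1.3.**

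| Week 1 SD | Residual correlation | Week 1 weight | Common slope | Extra variance, Week 12 | Extra variance, overall |
|---|---|---|---|---|---|
| 1.3 | AR(1) 0.90 | 1.27 | −0.15 | 1.9% | 1.9% |
| 1.3 | AR(1) 0.95 | 1.88 | −0.07 | 3.3% | 3.2% |
| 1.3 | equal, 0.7 | 1.01 | −0.06 | 3.5% | 4.0% |
| 1.8 | AR(1) 0.90 | 0.75 | −0.23 | 0.9% | 0.5% |
| 1.8 | equal, 0.7 | 0.62 | −0.15 | 1.9% | 1.5% |
| 2.4 | AR(1) 0.90 | 0.31 | −0.30 | 0.3% | <0.1% |
| 2.4 | equal, 0.7 | 0.05 | −0.35 | 0.1% | <0.1% |

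Arithmetic for the third row: V = 1.3² = 1.69; Week 12 residual variance = 2.4² − 0.40² × 1.69 = 5.49; extra variance = 1.69 × (0.40 − 0.06)² / 5.49, about 3.5%.

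With baseline SD 1.2-1.4 and Week 1 SD 1.2-1.4, the extra variance is 1.4-4.2% at Week 12 and 1.3-5.0% overall. Much steeper slopes (−0.10 to −0.50) raise it to as much as 11-13%.

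**5. Power at Week 12.** The residual SD is √5.49 = 2.34. Week-specific slopes give 82.1%. With the variance inflated by 1.9% to 3.5%, the common slope gives 81.4% to 80.8%. Over the grid just described, the gap is 0.5 to 1.6 points and the common-slope model never falls below 80.7%.

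**6. One realised imbalance.** A 2-SE baseline imbalance is 2 × 1.3 × √(2/92) = 0.38 points. With Week 1 SD 1.3, the adjustment error is 0.38 × (0.40 − 0.15) to 0.38 × (0.40 − 0.06), or 0.10-0.13 points at Week 12. The corresponding error overall is 0.07-0.10 points. This is the loss in step 4 seen conditionally, not a second loss.

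**7. Check by simulation.** Unstructured MMRMs were fitted to simulated trials of 4 × 92 patients (150 runs, Week 1 SD 1.3, baseline SD 1.4, residual correlation 0.6 plus 0.4 times AR(1) 0.7). The common slope averaged −0.11. Model SEs with common versus weekly slopes were 0.349 versus 0.344 at Week 12 and 0.266 versus 0.263 overall. Bias differed between the two models by at most 0.006.

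**8. Fallback.** Under a fitted compound-symmetry model, every week has weight 1/12. The common slope is then the mean slope, and the complete-data loss for the overall effect is zero. At Week 12 it is 1.69 × (0.40 − 0.333)² / 5.49, about 0.14%.

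**The case against.** The strongest reply is that a common baseline slope is a legitimate MMRM and that this point asks for a refinement. Randomisation keeps the comparison unbiased, and the model SEs rise with the misfit, so inference remains honest. SAP Appendix 1 describes the study as hypothesis generating and cites sample size as a limit on covariates. All of this stands except the sample-size argument, which carries little weight here: the model already estimates 4 × 12 = 48 treatment-by-week means and 12 × 13 / 2 = 78 covariance parameters.

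A reader might infer four stronger claims, none of which the documents support.
- **Week 1 sets the slope, and that slope is wrong.** This needs weekly SDs, correlations and slopes. The documents give only the Week 12 SD. The Week 1 weight falls below 0.4 if the SD is constant, and there is no loss if the true slope is constant.
- **The planned 80% is eroded.** That figure comes from an unadjusted t-test, and the planned model still meets it in the central cases.
- **The adjustment error in step 6 is a bias against the 1.0-point target.** It is conditional on a roughly 1-in-20 imbalance and averages to zero.
- **The loss carries over in full to every endpoint using this form.** IBS-SSS has post-baseline values only at Weeks 4, 8 and 12, so it has no Week 1 slope. The BM-related severity rating runs only from 1 to 5. The pain figures cannot be transferred to either.

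**Conclusion.** The point holds as a low-cost improvement, not as the correction of an error. Both documents fix one baseline slope for 12 weeks, and the mechanism by which Week 1 can dominate it is real. For pain, the likely cost is about 1.5-5% of variance, or roughly 0.5-1.5 power points at Week 12. This rests on an assumed baseline SD of 1.2-1.4, a change SD that roughly doubles from Week 1 to Week 12, and slopes steepening from −0.15 to −0.40.

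The loss shrinks to about 0.5-2% if the Week 1 SD is 1.8, and to nearly nothing if weekly SDs or slopes are near constant. For discomfort, bloating and cramping, which have no entry range, it could be larger: a simulation with symptom-level SD of about 2.2 and 20% dropout gave 8% (95% interval 5-12%). Those inputs are also assumptions.

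**What to change.** In SAP 7.8.9.2, specify the fixed effects as treatment, week, treatment-by-week, baseline and baseline-by-week. Carry the new term into the weekly change-from-baseline MMRMs in 7.8.9.4 (discomfort, bloating, cramping) and 7.8.10. Treatment Satisfaction and BM-related Symptom Change have no baseline in the model and need no change. A baseline-by-visit term for IBS-SSS in 7.8.12 is optional. Record the change under methodologic changes in Appendix 1.

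The cost is 11 additional fixed-effect parameters for about 368 patients and up to 368 × 12 = 4,416 patient-weeks, with no new data. If the slope is in fact constant, practically nothing is lost.
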